5.3 Analysis of seroconversion

We will perform analyses similar to those of Section 5.1, instead using the binary indicator of *seroconversion* as the outcome, as defined by at least a four-fold rise from baseline in titer within *any* of the four antigens. Correspondingly, we will utilize a logistic link instead of an identity link.

5.4 Effect modification

We will evaluate evidence of effect of vaccination on HAI response is modified by time post-transplant, age, or GVHD status by including (and subsequently testing) appropriate interaction terms in the model described in 5.1 (log-transformed continuous titer value).

5.5 Analysis of study repeaters

We will perform analyses similar to those described in Section 5.1, 5.2, and 5.3 in the RAS, using both their first and second year of data.

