Randomization to HD-TIV or SD-QIV was frequency-matched within each site to ensure balance between the groups and was implemented using the Randomization Module within Vanderbilt's REDCap database. For subjects \geq 12 months post-transplant, randomization was stratified on

treatment for graft versus host disease (GVHD) with systemic steroids. For subjects < 12 months post-transplant, randomization was stratified on meeting any of the following: (a) treatment for GVHD with systemic steroids, (b) history of alemtuzumab, (c) history of anti-thymocyte globulin, (d) receipt of a cord graft, (e) haploidentical transplant, or (f) post-transplant cyclophosphamide. Repeaters retained randomization from initial enrollment and were *not* re-randomized.

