1.2 Study objectives

Immunogenicity and safety objectives are organized into subsections below. To avoid repetitive language, *all* objectives apply to the target study population (namely, pediatric HSCT recipients).

1.2.1 *Objectives for HAI immunogenicity outcomes*

The primary objective is to determine whether two doses of HD-TIV is associated with a higher geometric mean HAI titer to either influenza A antigen (H1N1 and H3N2, evaluated separately) compared to two doses of SD-QIV.

The secondary objectives pertaining to HAI immunogenicity outcomes are as follows:

- To determine whether two doses of HD-TIV is associated with a higher geometric mean HAI titer to influenza B antigens as compared to two doses of SD-QIV.
- To determine whether two doses of HD-TIV is associated with higher odds of seroconversion or seroprotection in *any* HAI antigen as compared to two doses of SD-QIV.
- To compare HAI immunogenicity for each antigen between the following groups: (a) one dose of HD-TIV vs. one dose of SD-QIV, (b) one dose of HD-TIV vs. two doses of HD-TIV, and (c) one dose of SD-QIV vs. two doses of SD-QIV.

The tertiary objectives pertaining to HAI immunogenicity outcomes are as follows:

- To compare HAI immunogenicity for each antigen between the one dose of HD-TIV and two doses of SD-QIV.
- To determine whether time post-transplant, subject age, or GVHD status (presence/absence) modifies the association between vaccination group and HAI response.
- To characterize the relationship between HAI titers, ex-vivo T and B cell phenotype, and ex-vivo influenza-specific T and B cell response in subjects receiving either HD-TIV or SD-QIV.
- To compare HAI immunogenicity outcomes between treatment groups (one dose or two doses of HD-TIV vs. one dose or two doses of SD-QIV, respectively) among those enrolled for a second year (repeaters).

1.2.2 *Objectives for safety outcomes*

The primary objectives for safety outcomes are to compare the frequency/severity of solicited local injection site adverse events (AEs) and systemic AEs between HD-TIV and SD-QIV following the first dose and following the second dose. The secondary objective is to compare safety outcomes between treatment groups among those enrolled for a second consecutive year (repeaters).

1.2.3 *Further exploratory objectives*

- To compare the persistence of HAI and microneutralization (MN) titers between HD-TIV and SD-QIV across all four antigens seven months after the final vaccine dose.

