- To compare MN and NAI responses between subjects receiving HD-TIV and SD-QIV in the first year.
- To compare MN and NAI titers between treatment groups (two doses of HD-TIV vs. two doses of SD-QIV) among those enrolled for a second year, and compare them to HAI responses.
- To compare influenza virus detection during influenza season between treatment groups (two doses of HD-TIV vs. two doses of SD-QIV).
- To evaluate the correlation between HAI and baseline MN responses.

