5. STATISTICAL ANALYSES FOR IMMUNOGENICITY OUTCOMES

This section presents plans for analysis corresponding to each of the primary, secondary, and tertiary objectives listed in Section 1.2.1. We utilize the following general notation to describe models of interest:

• i : indicator of subject• t : indicator of visit ($t = 2, t = 3$)• X : randomized group (0 = SD, 1 = HD)• Y : titer outcome	
• \mathbf{L} : pre-treatment covariates• γ_i : subject-specific random effect• γ_S : study site random effect• ε_{it} : error term
---	---

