5.1 Analysis of continuous HAI titer responses

We will use mixed effect models to analyze continuous titers. All comparisons will be made on the geometric mean ratio scale. Consider the following model form:

$$\log(Y_{it}) = \beta_0 + \beta_1 \mathbf{1}(X = 1) + \beta_2 \mathbf{1}(t = 3) + \beta_3 \mathbf{1}(t = 3; X = 1) + \boldsymbol{\beta}_L \mathbf{L} + \gamma_i + \gamma_S + \varepsilon_{it},$$

under which all primary and secondary aims pertaining to continuous HAI titer outcomes can be addressed. The parameters of this model and the comparisons to which they correspond are summarized in Table 3.

Any continuous variables (e.g., time post-transplant and log-transformed baseline titer) used for adjustment will be flexibly modeled using natural cubic splines with knots at the 25th, 50th, and 75th percentiles.

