8. TABLES

TABLE 1: STUDY SITES

#	Site
1	Vanderbilt University
2	Seattle Children's Hospital
3	Children's Hospital of Philadelphia (CHOP)
4	Children's Mercy Hospital
5	Cincinnati Children's Hospital
6	Nationwide Children's Hospital
7	St. Jude Children's Research Hospital
8	UCSF (University of California San Francisco) Benioff Children's Hospital
9	Baylor School of Medicine, Texas Children's Hospital

TABLE 2: DEFINITION OF ANALYSIS SETS

#	Analysis set	Description
1	All randomized (ARAS)	All participants randomized into the study, for use in by-subject listings.
2	Full (FAS)	All participants who (1) are randomized into the study and (2) have received at least 1 dose of either vaccine.
3	Safety (SAS)	All participants who (1) are randomized into the study and (2) have completed at least one memory aid.
4	Repeating (RAS)	All participants who are (1) randomized into the study and (2) received at least one vaccination as a repeater.

TABLE 3: PARAMETERS FOR MIXED MODEL OF INTEREST

#	Comparison	Visit	Comparison	Parameter	Null hypothesis	Classification
1	2 doses HD-TIV 2 doses SD-QIV	3 3	Between-group	$\exp(\beta_3)$	$H_0: \beta_3 = 0$	Primary
2	1 dose HD-TIV 1 dose SD-QIV	2 2	Between-group	$\exp(\beta_1)$	$H_0: \beta_1 = 0$	Secondary
3	1 dose SD-QIV 2 doses SD-QIV	2 3	Within SD-QIV	$\exp(\beta_2)$	$H_0: \beta_2 = 0$	Secondary
4	1 dose HD-TIV 2 doses HD-TIV	2 3	Within HD-TIV	$\exp(\beta_2 + \beta_3)$	$H_0: \beta_2 + \beta_3 = 0$	Secondary
5	1 dose HD-TIV 2 doses SD-QIV	2 3	Between-group	$\exp(\beta_2 - \beta_1)$	$H_0: \beta_2 - \beta_1 = 0$	Tertiary

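### Does using both years of repeater data without a year-by-arm term hide the second-season HD-TIV versus SD-QIV effect?

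*SAP*

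**What the plan says.** SAP Section 5.5 is one sentence. It carries the analyses of titer, seroprotection and seroconversion over to the repeating analysis set (RAS), "in the RAS, using both their first and second year of data". It asks for similar analyses, not for the identical model.

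The Section 5.1 model has arm, visit (2 or 3), their interaction, pre-treatment covariates, and random effects for subject and site. It is presented as the model "under which all primary and secondary aims pertaining to continuous HAI titer outcomes can be addressed". The repeater comparison in SAP Section 1.2.1 is neither primary nor secondary: it is listed as tertiary. Table 3, "PARAMETERS FOR MIXED MODEL OF INTEREST", has no year-specific contrast. Section 5.4 names time post-transplant, age and GVHD status as effect modifiers, not study year. Under Section 1.1.4, "Repeaters retained randomization from initial enrollment", so arm is constant within a child across both seasons.

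Several places deal with the years explicitly:

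- SAP Section 1.2.3 has one microneutralization (MN) and neuraminidase inhibition (NAI) objective for the first year ("To compare MN and NAI responses between subjects receiving HD-TIV and SD-QIV in the first year") and another "among those enrolled for a second year, and compare them to HAI responses".
- SAP Section 6.2 selects repeaters for safety by their second-year memory aids.
- SAP Section 7.5 evaluates repeaters at the baseline visit of each year.
- Protocol Section C.2.b lists, as secondary, an objective on HAI and MN response over two consecutive years.

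**The concern.** Repeaters are the only children in this trial who can show whether the high-dose advantage persists, grows or fades in a second season. Section 5.5 points to a model with no year index. Taken literally, it puts four post-vaccination titers per child (two visits in each of two years) into a model that returns one arm ratio per visit. That ratio mixes the seasons and could be reported as a second-season effect when half of it comes from the first. A year main effect among the covariates would not separate them; only an interaction of year with arm does.

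There is also a concern about timing. SAP Section 1.3 ties the primary and secondary unblinded analyses to a finalized SAP and does not mention tertiary ones. An unspecified contrast might therefore be picked after the yearly and pooled results have been seen.

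**Working it through.** The documents state no figure for the repeater analysis, so there is nothing to reproduce. They give no number of repeaters, titer variance, between-year correlation or yearly effect; all of these are assumed below. The visit 3 contrast used is the total arm difference at that visit, β1 + β3.

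**1. What a literal stack estimates.** Let δ1 and δ2 be the log arm differences at a given visit in years 1 and 2. With equal data from each year and no year-by-arm term, the model estimates (δ1 + δ2)/2, so

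stacked GMR = √(GMR year 1 × GMR year 2).

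A year main effect shifts both arms alike and leaves this unchanged.

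| Year 1 GMR | Year 2 GMR | Stacked | Stacked ÷ year 2 |
|---|---|---|---|
| 2.0 | 1.0 | √2.00 = 1.41 | 1.41 |
| 2.0 | 1.5 | √3.00 = 1.73 | 1.15 |
| 1.5 | 1.3 | √1.95 = 1.40 | 1.07 |
| 1.5 | 1.5 | √2.25 = 1.50 | 1.00 |

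Mixed-model simulation (100 per arm, 60 replicates, random intercept per child) agrees. True 2.0 then 1.0 gave 1.43, and true 1.0 then 2.0 gave 1.46, so the stacked fit cannot tell opposite patterns apart. True 1.5 in both years gave 1.54.

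**2. What year terms recover.** Add year, year-by-arm (β5), year-by-visit and year-by-arm-by-visit (β6). The second-season ratio is then exp(β1 + β5) at visit 2 and exp(β1 + β3 + β5 + β6) at visit 3. In the same simulations this gave 1.99 and 1.03 for true 2.0 and 1.0, and 1.03 and 2.06 for true 1.0 and 2.0. Only analysis code has to change; no new data are needed.

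**3. How large the shift is beside the noise.** Assume 35 repeaters per arm, ln SD 1.5 and between-year correlation r = 0.6.

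- One year: SE = 1.5 × √(2/35) = 0.359. With t = 1.995 on 68 df, the 95% CI factor is exp(1.995 × 0.359) = 2.05.
- Pooled: the variance is multiplied by (1 + r)/2 = 0.8, so SE = 0.359 × √0.8 = 0.321 and the factor is exp(1.995 × 0.321) = 1.90.
- At 20 per arm the factors are 2.61 and 2.36; at 50 per arm, 1.81 and 1.70.

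Shifts of 1.07 or 1.15 are small beside a single-year CI factor of about 2. The shift of 1.41 needs the effect to vanish completely in the second season.

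**4. What pooling gains when the seasons agree.** If both yearly GMRs are 2.0, the pooled contrast is unbiased. Power is 57% against 48% for one year alone (52% to 66% pooled for r from 0.8 to 0.3).

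**5. What the wording allows.** A separate fit for each year uses both years' data. So does a joint model with year interactions, and so does a pooled model. Section 5.5 excludes none of them.

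**6. The year 2 baseline.** The documents nearly settle this. Blood is drawn at visit 1 of each season before vaccination (Protocol Section C.14). The strain lists in Protocol Section C.10.b change at least one influenza A component between every pair of consecutive seasons: H1N1 from 2016-17 to 2017-18, H3N2 from 2017-18 to 2018-19, and both from 2018-19 to 2019-20. A four-fold rise in year 2 is naturally measured from that season's own pre-vaccination titer.

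**The case for a change.** The strongest case for changing the text is that no listed parameter is a second-season effect. The Section 1.2.1 objective concerns children enrolled for a second year, and adding a sentence would cost almost nothing. The algebra behind this is right: a literal stack averages the seasons, and a year main effect does not help. It is also true that the target is not stated outright. The tertiary objective can be read as naming a population or as naming a season, while the protocol's objective speaks of two consecutive years.

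That ambiguity works in both directions. If the target is the effect over two years, the pooled ratio answers it, with better precision. If it is the second season, SAP Sections 1.2.3, 6.2 and 7.5 show authors who already distinguish the years, which makes a pooled-only analysis an unlikely reading. Section 7.5 concerns cell phenotype, so it indicates habit and does not settle Section 5.5.

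The worry about later choice carries little weight. Silence in Section 1.3 on tertiary analyses is not permission to select among results. Giving the yearly ratios with the pooled one, as is normal for such a subset, leaves nothing to select. The figures cover log titers only; the logistic versions for seroprotection and seroconversion were not examined, and three-way interactions there could be unstable in a small subset. That is a reason to leave the analyst some freedom.

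**Conclusion.** No change is needed. Section 5.5 leaves a detail open: whether the repeater comparison is reported by year, pooled, or both. A single stacked ratio presented as a second-season effect would be misleading, but the SAP does not prescribe that, and its wording accommodates the sensible analyses. An analyst can be expected to show the HD-TIV to SD-QIV ratio at visits 2 and 3 for each season, with the pooled estimate beside it and each season's own baseline.

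The size is modest and entirely assumed. The averaging distorts the second-season ratio by a factor of 1.07 to 1.15 in the milder cases and 1.41 if the effect disappears in year 2, against a single-year CI factor of about 2.05 at 35 per arm, ln SD 1.5. The objective is tertiary in the SAP, is confined to the repeater subset, and does not affect the primary comparison. The conclusion would differ only if the SAP required one pooled ratio and labelled it a second-season effect, which it does not.

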6. STATISTICAL ANALYSES FOR SAFETY OUTCOMES

6.1 Statistical analyses for safety outcomes

We will provide descriptive statistics (N, missing, mean, standard deviation, and quartiles) on solicited local and systemic AEs, overall and by randomized treatment group in the SAS.

Further, we will use a mixed model to separately compare the odds of local/systemic events at each visit between treatment groups.

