### **m. Blinding:**

All study staff, subjects, and their parent/guardians will be blinded to which vaccine the subject will receive, except for an un-blinded vaccinator. This individual will not inform the study team, subjects, and/or their parent/guardians which vaccine they administered to the subject. The un-blinded vaccinator will not participate in any other study activities. If the study vaccine is provided in a blinded manner, then research staff will be able to administer the vaccine, and an un-blinded vaccinator will not be necessary. The pharmacy will be un-blinded and will have a record of which vaccine was given to each subject.

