2. GENERAL CONSIDERATIONS FOR DATA ANALYSES

2.1 Estimands of interest

All primary analyses will be intention-to-treat (ITT) in nature, maintaining fidelity to randomized group. Per-protocol analyses may be performed as a sensitivity analysis.

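### Solicited adverse events are tabulated by randomised group with no rule for the vaccine actually received; any wrong-product dose would be credited to the wrong vaccine

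*SAP*

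**What the plan says.** **Tables.** SAP 6.1 gives descriptive statistics on solicited local and systemic events "overall and by randomized treatment group in the SAS".

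**Model.** The next sentence of 6.1 says "we will use a mixed model to separately compare the odds of local/systemic events at each visit between treatment groups". It does not say whether the groups are as randomised or as received. The notation in SAP section 5, written for the immunogenicity models, defines X as "randomized group (0 = SD, 1 = HD").

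**Analysis set.** SAP Table 2 defines the safety set as "All participants who (1) are randomized into the study and (2) have completed at least one memory aid". That settles who is in the set, but not under which vaccine each child is counted.

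**General rule.** SAP 2.1 states "All primary analyses will be intention-to-treat (ITT) in nature, maintaining fidelity to randomized group" and makes no exception for safety. The only alternative it offers is "Per-protocol analyses may be performed as a sensitivity analysis".

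**Repeaters.** SAP 6.2 follows 6.1.

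**Protocol.** Protocol 17.c speaks of each group without further definition. On records, Protocol 16.m says "The pharmacy will be un-blinded and will have a record of which vaccine was given to each subject".

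**The concern.** The safety objective in SAP 1.2.2 compares the two vaccines separately after the first and the second dose. Injection-site pain, redness and swelling depend on what was injected, not on what was allocated. Analysis by randomised group suits the superiority question on titres. For reactogenicity it would place a reaction to HD-TIV, given in error to a child randomised to SD-QIV, in the SD-QIV column.

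Such misclassification would, on average, pull the two columns together. Hypothesis 2 in the protocol expects a safety profile similar to that of the standard vaccine, so the bias would lie in the direction of the trial's own expectation. The opportunity for error exists: pharmacies at nine institutions supply two vaccines over four seasons, with two doses per child per season. The rule is best settled before unblinding, because choosing it once an error is known would be a post hoc decision about safety data.

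**Working it through.** **Is there an as-received rule anywhere?**

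| Place | Grouping stated |
|---|---|
| SAP 6.1, tables | Randomised group, explicit |
| SAP 6.1, mixed model | Treatment groups, not defined |
| SAP section 5 notation | X is the randomised group |
| SAP 6.2 | As in 6.1 |
| SAP 2.1 | Randomised group for all primary analyses; optional per-protocol sensitivity analysis |
| SAP Table 2, safety set | Membership only |
| Protocol 17.c | Each group, not defined |

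None of these assigns a child to the vaccine received. A per-protocol analysis, if done, might drop a misdosed child instead of moving the reaction to the vaccine given.

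**How large could the effect be?** The documents give no expected adverse event rates and no count of wrong-product doses, so there is no plan figure to reproduce. What follows is illustration.

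Inputs:
- 100 children per arm (Protocol 17.a); 80 per arm after the 20% dropout assumed there (100 × 0.8).
- Event rates of 60% on HD-TIV and 40% on SD-QIV: assumption. True difference D = 20 points.
- m = share of an arm given the other vaccine: assumption, unrelated to the child's own risk of a reaction.

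Formulas for the expected difference when tabulated by randomised group:
- same share m in both arms: D × (1 − 2m)
- share m in one arm only: D × (1 − m)

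Worked case, m = 0.02 in both arms:
- randomised to HD-TIV: 0.98 × 60 + 0.02 × 40 = 59.6%
- randomised to SD-QIV: 0.98 × 40 + 0.02 × 60 = 40.4%
- difference: 59.6 − 40.4 = 19.2 points

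If only the HD-TIV arm is affected: 59.6 − 40 = 19.6 points.

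| Cross-dosed per 100 | Both arms (points) | One arm (points) |
|---|---|---|
| 0 | 20.0 | 20.0 |
| 1 | 19.6 | 19.8 |
| 2 | 19.2 | 19.6 |
| 5 | 18.0 | 19.0 |
| 10 | 16.0 | 18.0 |

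Tabulation by vaccine received restores 20 points in expectation.

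**Per child.** One misdosed child in an arm of 100 shifts that arm's expected rate by 20/100 = 0.2 points. The maximum is 1/100 = 1 point, reached only when the child's outcome differs from what it would have been on the allocated vaccine.

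**Rare events.** Suppose there is one Grade 3 reaction and it occurs in a misdosed child. A table that should read 1 against 0 then reads 0 against 1. The between-arm difference moves by about 1/100 + 1/100 = 2 points, or 1/80 + 1/80 = 2.5 points at 80 per arm. If events are spread evenly over children, the chance that the single case falls on a misdosed child is about m, so about 2% in the worked case.

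**The case against.** The strongest reply is that the harm is hypothetical. No passage reports, expects or counts a wrong-product dose. A reader might infer from the number of sites, seasons and repeaters that errors occurred, but the documents do not support that. Repeaters keep their study ID and randomisation number (Protocol C.4.B), and SAP 1.1.3 says, in the past tense, that they received the formulation to which they were first randomised. That describes the design and does not prove that no error occurred, but it weakens the repeater route.

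A reader might also infer that serious events could be misjudged. The documents do not support this either. Serious events are assessed individually by investigators and the independent safety monitor (Protocol 16.h and 16.i), and the DSMB may ask for one subject to be unblinded. The halting rules in 16.j count subjects across the trial, not by arm. None of these depends on the grouping in SAP 6.1.

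Three further points stand. The word randomised is explicit only for the descriptive tables; for the mixed model it is an inference from the section 5 notation. No equivalence or non-inferiority test of safety is planned, so no formal conclusion of similar safety turns on slight attenuation. And the documents do not say that the pharmacy record would capture an error made at administration, or that it enters the analysis database.

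What the reply does not remove is the gap: the question is about the product injected, the stated grouping is the allocation, and no as-received rule exists.

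**Conclusion.** The point holds as a conditional gap and a cheap improvement, not as an error known to distort the results. SAP 6.1 fixes the safety tables by randomised group, 6.2 follows, and the mixed model probably does too. If any child received the other vaccine at a dose, that child's reactions would be credited to the wrong product and the comparison would tend towards no difference. With no misdosing, the two tabulations are identical.

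For common events the size is small: 0.8 of 20 points lost with 2% cross-dosed in both arms, 0.4 points if only one arm is affected. These figures rest on assumed rates of 60% and 40% and assumed error shares. The factor 1 − 2m applies only when both arms have the same error share. It would be too strong to say that each misdosed child moves the result by a full point, since that is the maximum, or that a lone Grade 3 event is likely to change columns.

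**What to change.** In SAP 6.1 state, for both the tables and the mixed model, that each post-dose period is analysed under the vaccine actually received at that dose, taken from the pharmacy and administration records. State the same in 6.2 for repeaters. List every child whose vaccine at any dose differed from allocation. Show the as-randomised table as a supplement only if the list is not empty.

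The cost is a few lines of SAP wording and no new data collection, provided the vaccine given at each dose can be traced. The small downside is that dispensing and administration records must be linked to the analysis database after unblinding. The immunogenicity analyses stay by randomised group.
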